13.7 Reporting and Exclusions

All patients who complete the baseline and 6 week assessments will be included in the analyses.

13.7.1 Evaluation of Toxicity

All participants will be evaluable for toxicity from the time of their first treatment.

13.7.2 Evaluation of the Primary Efficacy Endpoint

Since the primary end-point is assessing change in HR from baseline to 6 weeks, we will only include those patients who complete both the baseline and 6 week visit for evaluation of the primary efficacy end-point. However, we will have HR data at the 2 week titration visit and will report this if there is a significant rate of study withdrawal or loss to follow up in the ivabradine group.

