4.3 General Guidelines for Other Investigative Sites: N/A

4.4 Registration Process for Other Investigative Sites: N/A

5. TREATMENT PLAN

5.1 Treatment Regimen

A total of 60 eligible patients will be randomized to ivabradine or placebo. Ivabradine or placebo will be administered for a total of 6 weeks. Treatment will be administered on an outpatient basis. On assessment days, no dose holds will occur. Reported adverse events and potential risks are described in Section 7.

Ivabradine will be started at a dose of 5 mg p.o. twice daily with meals. The patient will then be assessed after 2 weeks and the dose will be adjusted as shown in the Table below:

Heart Rate	Dose Adjustment
> 60 bpm	Increase dose to 7.5 mg p.o. twice daily
50-60 bpm	Maintain dose at 5 mg p.o. twice daily
< 50 bpm or signs and symptoms of bradycardia	Decrease dose to 2.5 mg p.o. twice daily

If the patient continues to have symptomatic bradycardia or HR < 50 on 2.5 mg twice daily, ivabradine will be discontinued.

If symptomatic bradycardia occurs on ivabradine 7.5 mg or 5 mg twice a day at any point in the study, without objective hemodynamic compromise (SBP > 80 mm Hg), the medication can be resumed at a lower dose (2.5 mg reduction) after a 24 hour drug-free interval (i.e. 1 missed dose). If symptomatic bradycardia persists despite dose reduction, then the study drug will be further reduced by 2.5 mg or discontinued as per the discretion of the investigator. A maximum of 2 dose reductions would be allowed for patients on 7.5 mg twice daily and 1 dose reduction for those on 5 mg twice daily. Patients requiring dose reduction will not have a subsequent dose escalation at any point during the study.

Placebo will be used in a similar manner. Patients will be maintained on the best tolerated dose for a total of 4 weeks.

Patients randomized to either ivabradine or placebo will be asked to maintain a drug diary as detailed in Appendix B to assess compliance.

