5.3.1 CTEP and/or CIP IND Agent(s), or other IND agent: N/A

5.3.2 Other Agent(s): N/A

5.3.3 Other Modality(ies) or Procedures

All patients will have a standard 12 lead EKG performed at the screening, baseline, 2 week and 6 week visits.

All patients will undergo exercise treadmill testing at the baseline and 6 week visits.

All patients will have a 24 hour ambulatory Holter monitor placed at the baseline and 6 week visits.

All patients will complete the SF-36 quality of life questionnaire at the baseline and 6 week visits.

Due to cost constraints, a subset of patients (n=30) will undergo further sophisticated autonomic function testing at the baseline and 6 week visits. Depending on scheduling limitations, they may have to return for a second day at each of these visits to complete the additional autonomic function tests.

a) Exercise treadmill testing

All exercise stress tests will be performed in the cardiovascular stress testing laboratory at Brigham and Women's Hospital by trained exercise physiologists under the supervision of a staff

cardiologist. Patients will avoid consumption of all caffeine containing products for 24 hours prior to exercise treadmill testing. All patients will undergo exercise treadmill testing using a symptom-limited Bruce protocol according to established guidelines.¹⁸ Exercise will be continued until one or more of the following endpoints: exhaustion, symptom limitation, $\geq 85\%$ of age-predicted maximal HR, ≥ 10 mmHg drop in systolic blood pressure (SBP) from baseline, sustained ventricular tachycardia, ST-segment depression ≥ 3 mm measured 80 msec after the J junction, or ST-segment elevation of ≥ 1 mm.

b) 24 Hour Ambulatory Holter Monitor

All patients will have a 24 hour ambulatory Holter monitor placed at baseline prior to study drug initiation and at the 6 week time point, prior to study drug termination. Holter monitors will be placed by the cardiology department at Brigham and Women's Hospital. Patients will be asked to return the Holter monitor in person or via mail to Brigham and Women's Hospital.

c) SF-36 Quality of Life Questionnaire

All patients will be asked to complete short form 36 (SF-36) quality of life healthcare questionnaires at the baseline and 6 week visits.

d) Sophisticated autonomic function testing

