5.6 Criteria for Taking a Participant Off Protocol Therapy

Patients will receive ivabradine or placebo for a total of 6 weeks. Treatment may continue for 6 weeks or until one of the following criteria applies:

- Intercurrent illness that prevents further administration of treatment
- Unacceptable adverse event(s)
- Participant demonstrates an inability or unwillingness to comply with the oral medication regimen and/or procedure/documentation requirements
- Participant decides to withdraw from the protocol therapy
- General or specific changes in the participant's condition render the participant unacceptable for further treatment in the judgment of the treating investigator

Participants will be removed from the protocol therapy when any of these criteria apply. The reason for removal from protocol therapy, and the date the participant was removed, must be

documented in the case report form (CRF). Alternative care options will be discussed with the participant.

An ODQ Treatment Ended/Off Study Form will be filled out when a participant is removed from protocol therapy. This form can be found on the DF/HCC website at <http://www.dfhcc.harvard.edu/research/clinical-research-support/document-library-forms-sops-etc/>.

In the event of unusual or life-threatening complications, treating investigators must immediately notify the Overall PI, *[name]* at [contact] [name].

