- In the Ivabradine and chronic outcomes in heart failure (SHIFT) trial, the net reduction in heart rate with ivabradine was 10.9 (95% CI 10.4-11.4) bpm, with a standard deviation of 10.5 bpm. Thus, with a sample size of 27 patients in each group, we will have 95% power to detect this net reduction in heart rate assuming a probability of making a type I error of 0.05.¹² To allow for incomplete primary end point data due to withdrawals or loss to follow up, we will aim to recruit 30 patients in each group.
- With a sample size of 27 subjects in each group, we will have 90% power to detect a clinically meaningful improvement of 34% in exercise duration on treadmill testing assuming a probability of making a type I error of 0.05, an improvement in the placebo group of 12%, and a standard deviation of 24%.
- All patients will first be stratified into two groups according to pre-randomization treatment with beta-blocking agents. Patients within each beta-blocker group will then undergo four way randomization using permuted blocks, dividing the two strata into four groups each: ivabradine with sophisticated autonomic testing, placebo with sophisticated autonomic testing, ivabradine with no sophisticated autonomic testing, placebo with no sophisticated autonomic testing. These four groups will be created in a 1:1:1:1 ratio. Randomization will be performed by the ODQ at Dana Farber Cancer Institute.
- If patients are randomized into the sophisticated autonomic testing group and are not able to complete sophisticated autonomic function testing for any reason, but are willing to continue taking the study medication (ivabradine or placebo), they will be encouraged to continue taking part in all other study protocols for the duration of the study: twice daily ivabradine or placebo, history and physical exam, EKG, SF-36 questionnaire, exercise treadmill test, and 24 hour ambulatory holter monitoring.

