13.5 Analysis of Primary Endpoint

The primary end-point of this study is the change in resting HR with ivabradine, compared to placebo, in survivors of lymphoma with mediastinal involvement who were treated with mediastinal/mantle radiation and have a resting HR \geq 80 bpm.

We will calculate the change in resting HR (from EKGs) from baseline to 6 weeks for each patient in the study (n=60). An ANCOVA model (for normally distributed data) adjusting for the stratification factors (beta blocking agents [Yes, No], autonomic function testing [Yes, No]) or Quade test adjusting for the stratification factors (beta blocking agents [Yes, No], autonomic function testing [Yes, No]) (for non-normally distributed data) will be implemented to compare the change in resting HR with ivabradine versus placebo. A p value < 0.05 using a two-sided test will be considered statistically significant.

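### The primary analysis keeps only patients with both visits, has no missing-data method, and commits to reporting week-2 heart rate only after an undefined loss in one arm; the resulting bias is possible and probably modest

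*Combined protocol and SAP*

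**What the plan says.** **Analysis set.** Section 13.7 sets the general rule: "All patients who complete the baseline and 6 week assessments will be included in the analyses". Section 13.7.2 repeats it for the primary endpoint: "we will only include those patients who complete both the baseline and 6 week visit for evaluation of the primary efficacy end-point". Section 13.5 describes the same calculation as covering every patient and gives 60 as the number.

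**Missing data.** Section 13.1 expects "incomplete primary end point data due to withdrawals or loss to follow up, we will aim to recruit 30 patients in each group". Sections 13.3 to 13.7 describe no imputation, repeated-measures model or sensitivity analysis.

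**Week-2 HR.** Section 13.7.2 notes that HR from the titration visit will be available and that the team "will report this if there is a significant rate of study withdrawal or loss to follow up in the ivabradine group".

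**Stopping drug.** Section 5.1, repeated in section 6, says: "If the patient continues to have symptomatic bradycardia or HR < 50 on 2.5 mg twice daily, ivabradine will be discontinued". Section 5.6 adds other routes off therapy, including unacceptable adverse events and "Participant decides to withdraw from the protocol therapy".

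**Measurement after stopping.** Section 5.3.3 says: "All patients will have a standard 12 lead EKG performed at the screening, baseline, 2 week and 6 week visits". Section 5.7 follows participants to the end of the protocol. Section 5.8 lists loss to follow-up, withdrawal of consent for data submission and death as reasons to leave the study; stopping drug is not among them. Section 10 asks for week-6 tests before study drug ends.

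**The concern.** Randomisation balances the two groups of 30, not the subsets who return at week 6. The endpoint is HR, and one of the stated reasons for stopping drug is low HR or symptomatic bradycardia. If patients who stop for that reason also miss week 6, who is missing depends on the outcome, and it will do so more in one arm than in the other. Extra recruitment replaces the lost precision but does not restore comparability.

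The plan also leaves open which effect it estimates: the effect while on drug, or the effect in everyone assigned to ivabradine. The two can move in different directions. If the largest responders drop out, completers understate the on-drug effect. They still overstate the effect in all assigned patients if those who stopped return to baseline.

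Week-2 HR is the natural information to bring in, since it is scheduled for everyone. Yet the commitment to report it depends on a judgement about one arm, made once the loss is known and without a cut-off.

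**Working it through.** **Inputs from section 13.1.** Net HR reduction 10.9 bpm, SD 10.5 bpm, 27 evaluable and 30 recruited per arm, 95% power. Two-sided 0.05 is from section 13.5.

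**Step 1: the plan's own figure.** A two-sided t-test with 27 per arm has power 0.963, so the stated 95% reproduces. If 3 patients are lost from ivabradine only (27 against 30), power is 0.970. Precision is not the problem.

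**Step 2: how much loss is plausible?** No discontinuation rate is given. Section 13.1 gives two purposes for the extra patients. One sentence names withdrawals and loss to follow-up. Another, repeated in 13.2, also names screen failure and a baseline HR below 80 bpm. Loss after randomisation could therefore be below 3 per arm, so 1 to 3 of 30 is an assumption.

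A rough check on HR-driven stopping uses P(HR < 50) = Φ((50 − (b − 10.9))/10.5) for baseline b:

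| Baseline (bpm) | Probability | Expected of 30 |
|---|---|---|
| 80 | 0.0345 | 1.0 |
| 85 | 0.0109 | 0.3 |
| 90 | 0.0028 | 0.1 |

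This is nearer a dose-reduction count than a stopping rate, because drug is stopped for HR only if it stays below 50 on the lowest dose.

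**Step 3: completers against all assigned.** Assume ivabradine falls are N(10.9, 10.5), placebo change is 0, k of 30 are lost on ivabradine and none on placebo, and lost patients return to baseline. Then all-assigned effect = completer effect × (1 − k/30), and gap = completer effect × k/30. Three patterns of loss:

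- A: lost patients are average responders.
- B: the k largest week-2 falls are lost (assumed week-2 to week-6 correlation 0.6).
- C: the k largest week-6 falls are lost.

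B and C come from 200,000 simulated arms.

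| k | Pattern | Completers (bpm) | All assigned (bpm) | Gap (bpm) |
|---|---|---|---|---|
| 1 | A | 10.90 | 10.54 | 0.36 |
| 1 | B | 10.46 | 10.11 | 0.35 |
| 1 | C | 10.17 | 9.83 | 0.34 |
| 3 | A | 10.90 | 9.81 | 1.09 |
| 3 | B | 9.73 | 8.76 | 0.97 |
| 3 | C | 8.95 | 8.06 | 0.89 |

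With SE = 10.5 × √(2/30) = 2.71 bpm, the gaps run from 0.34/2.71 = 0.13 to 1.09/2.71 = 0.40 standard errors.

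**Step 4: what week-2 HR can repair.** A likelihood analysis using week 2, with k = 3 and 40,000 simulated trials of 30 per arm, gives 10.89 in A, 10.89 in B and 9.59 in C. The completer values in the same runs are 10.89, 9.72 and 8.94; the all-assigned values are 9.80, 8.75 and 8.05. Week-2 data recover the on-drug effect when loss follows week-2 HR (B) and recover it partly in C. They do not give the all-assigned effect in any pattern, so a separate sensitivity analysis is needed for unmeasured patients who stopped.

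**Step 5: the undefined trigger.** If each ivabradine patient had a 10% chance of loss (the 54-to-60 margin read wholly as loss), the chance of at least 3, 4, 5 or 6 missing of 30 would be 59%, 35%, 18% or 7%. Whether the commitment to report applies depends heavily on the unstated cut-off.

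**The case against.** The strongest reply is that this is a six-week phase II/pilot study in which few patients will be lost, and that the protocol already provides for most of what is asked. Much of that stands.

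- **Do patients who stop drug drop out of the primary analysis?** A reader might infer so, but the documents do not say it. Sections 5.3.3, 5.7 and 5.8 together imply a week-6 EKG off drug. The section 10 timing is most naturally read as applying to patients still on drug. What is missing is an explicit sentence.
- **Is week-2 EKG HR the only other HR information?** No. Section 10 schedules vital signs at every visit, section 5.3.3 has a Holter at baseline and week 6, and section 6 brings in patients with bradycardia symptoms after titration for an additional EKG.
- **Could the trigger change the primary result?** No. The endpoint stays at week 6, and the text does not say that week-2 HR is otherwise withheld. It only fails to commit to reporting it.
- **Is the 60 in section 13.5 a serious contradiction?** It may simply be planned enrolment, with 13.7.2 as the specific rule. The sections still need aligning.
- **Is 3 of 30 the planned loss?** The documents do not establish that (step 2). Returning every lost patient to baseline is also a bound, because someone lost to follow-up may still be taking drug.

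What does not fall away is the completers-only rule, the absence of any missing-data method, and the one-arm trigger without a threshold. The pilot label does not remove the point, because the study is randomised, double-blind and tested at two-sided 0.05.

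**Conclusion.** The point holds as a weakness in the analysis rule, not as a demonstrated bias or a sample-size error. Bias arises only if patients are missing at week 6 for reasons related to HR or treatment, and its direction depends on who is lost and which effect is meant. Under the assumed 1 to 3 ivabradine losses and none on placebo, the gap is about 0.3 to 1.1 bpm against a planned 10.9 bpm effect. That is too small to suggest that the trial's conclusion would reverse. The change is still worth making, because the visits and EKGs needed for a better analysis are already scheduled.

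**What to change.** 1. **Primary analysis.** Analyse by assigned arm all randomised patients with a baseline HR and at least one post-baseline EKG HR. Use a repeated-measures model of week-2 and week-6 HR with baseline HR and the two stratification factors, and take the week-6 difference as the estimate. Say what role the Quade test in 13.5 keeps. Say how patients are handled whose registration is cancelled under section 4.1 because they received no therapy. Align 13.5, 13.7 and 13.7.2.
2. **Week-6 EKG.** State that it is obtained and used whether or not study drug was stopped, and clarify that the section 10 timing applies to patients still on drug.
3. **Week-2 HR.** Report it in both arms unconditionally.
4. **Sensitivity analyses.** Add a return-to-baseline analysis for patients who stopped drug and have no week-6 EKG, because the repeated-measures model does not correct for them. Keep the completer analysis as a second sensitivity analysis.

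The cost is protocol and SAP wording, slightly more analysis work, and possibly a slightly smaller estimated effect. No new scheduled visit, test or patient is needed. The changes should be fixed before unblinding.

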APPENDIX A Birth Control Measures

A woman is considered to be of childbearing potential unless she meets at least one of the following criteria:

- Previous bilateral salpingectomy, bilateral salpingo-oophorectomy, or hysterectomy
- Premature ovarian failure confirmed by a specialist
- Pre-pubescence, XY genotype, Turner Syndrome, uterine agenesis
- Post-menopausal, defined as 12 consecutive months with no menses without an alternative medical cause

Women of Childbearing potential must use a reliable method of contraception during treatment with ivabradine and for an additional 2 weeks after the last dose of ivabradine. The use of the following options is regarded as highly effective contraception:

Option #1

One method from this list:
Combined (estrogen and progesterone containing) hormonal contraception: 
- Oral- Intravaginal- Transdermal- OR Progesterone-only hormonal contraception: 
- Oral- Injectable- Transdermal

Option #2

One method from this list:
Intrauterine device (IUD) Intrauterine hormone-releasing system (IUS)

Option #3

One method from this list:
Partner's vasectomy with medical confirmation of surgical success Bilateral tubal occlusion Sexual abstinence

APPENDIX B Drug Diary

Study Participant Self-Administration Study Drug Diary Dana-Farber/Harvard Cancer Center

--

Participant Identifier: _____
Protocol # _____
Study MD _____ Phone _____

STUDY DRUG INSTRUCTIONS:

Study Drug: Ivabradine

How Much: a) 2.5 milligrams,
b) 5 milligrams, OR
c) 7.5 milligrams

How Often: Twice daily

When: With breakfast and with dinner

SPECIAL INSTRUCTIONS:

- i) do not consume grapefruit, grapefruit juice, or any other form of grapefruit
- ii) do not consume starfruit
- iii) do not consume pomegranate, pomegranate juice or any other form of pomegranate
- iv) Store drug at room temperature and keep drug in provided pill bottle
- v) a dose should be considered missed if it has not been taken within 6 hours prior to the next scheduled dose. If you miss a dose or vomit after taking the medication, please make a note of this in your drug diary. Take your next dose at your regularly schedule time
- vi) if you experience any side effects, please note this in your drug diary. If these side effects interfere with your ability to carry out your daily activities, please contact the study staff.
- vii) please keep drug in provided pill bottle
- viii) bring any unused drug, your pill bottle, and this diary to your next clinic visit
- ix) do not crush, chew, or dissolve drug in water
- x) do not skip drug on days where you come to see your doctor
- xi) please update this diary daily

OTHER MEDICATIONS TAKEN

If you take a daily medication or supplement (prescribed or otherwise), please use one line per drug and indicate the start and stop dates under the "Date(s) Taken" section (i.e., 6/2/09 - 6/5/09).

Drug Name	Dose	Dates Taken	Reason Taken

Study Participant Initials _____

Date _____

FOR STUDY TEAM USE ONLY	
Staff Initials:	
Date Dispensed:	Date Returned:
# pills/caps/tabs dispensed:	# pills/caps/tabs returned:

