6. DOSING DELAYS/DOSE MODIFICATIONS

All patients will be started on ivabradine 5 mg po twice daily or placebo. Dose modifications will be made at the 2 week visit as indicated in the following table(s).

Heart Rate	Dose Adjustment
> 60 bpm	Increase dose to 7.5 mg p.o. twice daily
50-60 bpm	Maintain dose at 5 mg p.o. twice daily
< 50 bpm or signs and symptoms of bradycardia	Decrease dose to 2.5 mg p.o. twice daily

If the patient continues to have symptomatic bradycardia or HR < 50 on 2.5 mg twice daily,

ivabradine will be discontinued. Placebo will be used in a similar manner. Patients will be maintained on the best tolerated dose for a total of 4 weeks.

If symptomatic bradycardia occurs on ivabradine 7.5 mg or 5 mg twice a day at any point in the study, without objective hemodynamic compromise (SBP > 80 mm Hg), the medication can be resumed at a lower dose (2.5 mg reduction) after a 24 hour drug-free interval (i.e. 1 missed dose). If symptomatic bradycardia persists despite dose reduction, then the study drug will be further reduced by 2.5 mg or discontinued as per the discretion of the investigator. A maximum of 2 dose reductions would be allowed for patients on 7.5 mg twice daily and 1 dose reduction for those on 5 mg twice daily. Patients requiring dose reduction will not have a subsequent dose escalation at any point during the study.

Any patients with symptoms of bradycardia after drug titration will be brought in for an additional clinical evaluation and EKG.

Overdosage of ivabradine may lead to severe and prolonged bradycardia. In the event of bradycardia with poor hemodynamic tolerance, the drug should be withdrawn. Supportive treatment, including intravenous fluids, atropine, intravenous beta-stimulating agents (isoproterenol) or temporary pacing may be considered.

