8.1.7 Preparation

After randomization, ivabradine or matching placebo tablets will be supplied by the Investigational Drug Pharmacy at Brigham and Women's Hospital.

Active medication will be blinded using over-encapsulation in an empty gelatin capsule by the Investigational Drug Pharmacy at Brigham and Women's Hospital. The matching placebo will be a capsule filled with microcrystalline cellulose also prepared by the Investigational Drug Pharmacy at Brigham and Women's Hospital.

Both the patient and investigators will remain blinded to study drug assignment throughout the duration of the study.

8.1.8 Administration:

Medication will be taken P.O. twice daily with food. Medication will be taken outpatient. Pills should be swallowed whole.

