8.2 IND Agent #2: N/A

8.3 Other Agent #1: N/A

8.4 Other Agent #2: N/A

9. BIOMARKER, CORRELATIVE, AND SPECIAL STUDIES

9.1 Biomarker Studies: N/A

9.2 For IDE Protocols Only: Investigational Device Information: N/A

9.3 Laboratory Correlative Studies: N/A

9.4 Other Agent #2: N/A

10. STUDY CALENDAR

Baseline evaluations/tests are to be conducted within 1 week prior to start of protocol therapy. In the event that the participant's condition is deteriorating, laboratory evaluations should be repeated within 48 hours prior to initiation of therapy.

2 week study evaluations and drug up-titration should be administered within ± 3 days of the protocol-specified date, unless otherwise noted.

Week 6 study evaluations/tests should be conducted within ± 7 days of the protocol-specified date and should be completed prior to termination of study drug.

	Screening visit	Baseline	Week 2	Week 6
Agents:		Ivabradine vs. placebo	Ivabradine or placebo dose titration	Study End
Informed consent	X			
Demographics	X			
Medical history	X		X	X
Physical exam		X	X	X
Concurrent Meds	X	X	X	X
Vital signs	X	X	X	X
Height		X		X
Weight		X		X
Serum chemistry ^a	X			
EKG (as indicated)	X	X	X	X
B-HCG		X ^b		X ^b
Exercise stress test		X		X
24-hr ambulatory Holter monitor		X		X
SF-36 QOL questionnaire		X		X
Sophisticated autonomic function testing ^c		X		X
Adverse event evaluation		X-----X		
a: Review of SGOT [AST], SGPT [ALT], creatinine obtained within the last 12 months. b: Urine pregnancy test (women of childbearing potential). c: For subset of patients randomized to receive autonomic function testing				

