12.1.3 Confidentiality Protections

Data will be obtained from a complete history, physical examination, symptom limited exercise stress test, 24 hour ambulatory Holter monitor, cardiac autonomic testing, and a self-reported health related quality of life questionnaire (SF-36) before and after the 6

week treatment period. Data will also be collected from the 14-day safety visit. The data will be shared with investigators/personnel involved in the study and will be retained for at least 5 years after completion of the study. The data source files will be kept in a locked room in the cardiovascular offices at Brigham and Women's Hospital. The data will be stored in a de-identified manner in an encrypted Partners computer.

The identifiable information will not be reused or disclosed except as consistent with this protocol and signed HIPAA Authorization for Research.

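### Section 6 promises an evaluation and EKG for any bradycardia symptoms after titration, but diary item vi prompts a call only when a side effect limits daily activities

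*Combined protocol and SAP*

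**What the plan says.** Section 6 (Dosing Delays/Dose Modifications) states the safety rule without grading the symptoms: "Any patients with symptoms of bradycardia after drug titration will be brought in for an additional clinical evaluation and EKG". Two dosing rules in Sections 5.1 and 6 also depend on staff learning of symptoms:

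- **Reduction from 7.5 mg or 5 mg.** This is permissive and applies at any time in the study when there is no haemodynamic compromise: "the medication can be resumed at a lower dose (2.5 mg reduction) after a 24 hour drug-free interval".
- **Stop on 2.5 mg.** This is mandatory. If symptomatic bradycardia or a heart rate below 50 bpm continues on 2.5 mg twice daily, the drug is discontinued.

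Appendix B (Drug Diary), special instruction vi, has patients note any side effect in the diary. It then gives the condition for calling: "If these side effects interfere with your ability to carry out your daily activities, please contact the study staff". Item viii has the diary brought to the next clinic visit.

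Section 10 (Study Calendar) and Section 5.3.3 place EKGs at screening, baseline, week 2 and week 6. Section 12.1.3 names the only interim visit: "Data will also be collected from the 14-day safety visit". The calendar's adverse-event row runs as a continuous line across treatment but gives no contact method or interval.

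**The concern.** Section 6 can work between visits only if patients tell staff about their symptoms. The diary is the only patient-facing reporting instruction in the text available for review, and its prompt to call is narrower than the rule it has to serve. A patient who feels light-headed on the adjusted dose but carries on as usual falls under Section 6 and not under the diary's prompt. Acting exactly as instructed, that patient writes the symptom down and brings the diary to week 6.

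What is at stake is the timing of a safety response. The extra EKG, a decision to lower the dose, or the required stop on 2.5 mg could come at the end of treatment and not near the symptom. The expected toxicities in Section 7.7.1.1 include bradycardia, conduction disturbances and syncope, and patients on beta-blockers are enrolled (Section 13.3), so a prompt report has some value.

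**Working it through.** **Step 1: compare the two triggers.**

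| | Section 6 | Diary item vi |
|---|---|---|
| Symptoms covered | any bradycardia symptoms after titration | any side effect |
| Threshold | none | none to record; limits daily activities to call |
| Result | evaluation and EKG | diary entry, or a call if the threshold is met |
| When staff learn of it | not stated | at the call, or at the next visit (item viii) |

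The two agree for symptoms that limit daily activities. They part for milder ones.

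**Step 2: length of the gap.** Inputs are the nominal visit days (week 2 = day 14, week 6 = day 42) and the windows in Section 10: "2 week study evaluations and drug up-titration should be administered within ± 3 days of the protocol-specified date" and "Week 6 study evaluations/tests should be conducted within ± 7 days of the protocol-specified date".

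- Nominal gap: 42 − 14 = 28 days. This reproduces the 4 weeks that Section 5.3 gives for treatment after titration.
- Week 2 window: 14 − 3 = day 11 to 14 + 3 = day 17.
- Week 6 window: 42 − 7 = day 35 to 42 + 7 = day 49.
- Shortest gap: 35 − 17 = 18 days.
- Longest gap: 49 − 11 = 38 days.

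These are upper limits on the wait, reached when a mild symptom starts straight after titration. A symptom that starts later waits less.

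**Step 3: the dose in use during the gap.** At week 2 the dose goes to 7.5 mg if heart rate is above 60 bpm, stays at 5 mg at 50–60 bpm, and falls to 2.5 mg below 50 bpm or with bradycardia signs and symptoms. At the entry minimum of 80 bpm (Section 3.1.7) and the roughly 10 bpm reduction in Section 2.3, heart rate would be about 80 − 10 = 70 bpm, above 60. A typical ivabradine patient therefore moves to the top dose as the gap opens. The same figure suggests that bradycardia will not be common. A patient reduced to 2.5 mg at week 2 enters the same gap with no scheduled check of the mandatory stop rule until week 6.

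**Step 4: what week 6 still catches.** An EKG is done at week 6, and the 24-hour Holter is placed "at the 6 week time point, prior to study drug termination". A persistent rhythm problem would be seen on treatment. An episode that resolved earlier would not, and a finding at week 6 comes too late to guide dosing.

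**The case against.** The strongest reply is that the two texts do not contradict each other. Section 6 says what staff do once a patient has symptoms; it sets no reporting route and no deadline. Sections 5.1 and 5.3 describe the diary as a compliance record. Item vi says when a patient should call, does not say that other calls are unwelcome, and the form has a line for a study doctor's phone number. All of this stands. It is why the delay is only possible, and why this is not an error in the plan. It does not remove the mismatch: the one visible prompt to call still leaves out symptoms that Section 6 covers.

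Second, the consent text was not available for this review and may tell patients when to call. Section 3.2.3 shows that the plan uses consent counselling for advice, though there on drug interactions. This also stands. A reader might infer that patients are given no other instruction to report mild symptoms; the documents do not support that.

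Third, a reader might halve the 28-day gap and quote 14 days as the typical delay. That needs symptom onset spread evenly over the gap and patients who never call. The documents support neither, and onset soon after the dose change would give longer waits. A reader might also want a number of patients affected, but the documents give no rate of mild symptomatic bradycardia, so none is offered.

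Finally, the gain is limited to milder symptoms, since fainting would plausibly already meet the diary's threshold. That is correct.

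**Conclusion.** The point holds as a mismatch between a stated safety rule and the patient instruction that should trigger it. Evaluation, dose reduction or the mandatory stop on 2.5 mg could be delayed until week 6 for symptoms that do not limit daily activities. The longest such wait is 28 days nominally, or 18 to 38 days depending on where the two visits fall in their windows. This assumes that the patient does only what item vi prompts and that no consent text says otherwise.

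The consequence is modest. Reduction from 7.5 mg or 5 mg is at discretion, only patients above 60 bpm are raised, and a persistent problem would show at week 6. A reader might infer that patients are left unprotected or that the efficacy results are affected. The documents support neither: symptoms that limit daily activities already prompt a call, and no endpoint, sample size or power figure changes. It is a worthwhile, low-cost improvement.

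**What to change.** Reword diary item vi along these lines: *Write every side effect in this diary. If you feel dizzy, light-headed or close to fainting, or if you faint, call the study staff promptly, even if it is mild. For any other side effect, call if it gets in the way of your daily activities.* Align it with the consent form so that patients receive one message.

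The list leaves out slow pulse, which would draw patients' attention to the drug's effect in a trial where "Both the patient and investigators will remain blinded to study drug assignment throughout the duration of the study", and tiredness, which is non-specific in these survivors. The prompt therefore stays slightly narrower than Section 6, but it covers the milder symptoms most likely to go unreported.

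The cost is one changed instruction with IRB approval, plus some extra calls and unscheduled EKGs in both arms. Some calls will concern light-headedness unrelated to the drug, since Section 2.1 reports orthostatic hypotension in irradiated survivors. The documents do not allow the number of calls to be estimated. Section 6 already commits to the evaluations.
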